2.1.3 Efficacy Endpoints

Primary Efficacy Endpoint

The primary efficacy endpoint is the annualized change in new HO volume as assessed by low-dose, WBCT, excluding head. The annualized change in new HO volume will be compared between treated and untreated subjects. WBCT scans are performed at baseline, Month 12,

Month 24 and Month 36 in the NHS and at baseline, Month 6, Month 12, Month 18 and Month 24 in the MOVE Trial. WBCT scans may also be performed at the time of early study discontinuation.

As described in the MOVE Trial and NHS Independent Review Charter, HO volume is assessed by two independent readers blinded to study and timepoint, with adjudication by a third independent reader. HO volume is measured by body region with the baseline scan. The following 9 anatomical regions will be used to describe HO location:

- Right chest, neck, shoulder through mid-humerus
- Left chest, neck, shoulder through mid-humerus
- Mid Torso: torso below shoulder regions and above iliac crests
- Right arm: mid-humerus through hand
- Left arm: mid-humerus through hand
- Right hip: iliac crest, hip through mid-femur
- Left hip: iliac crest, hip through mid-femur
- Right lower leg: mid-femur through foot
- Left lower leg: mid-femur through foot

In post-baseline scans, the presence of new HO within each body region and, if present, the HO volume within the body region, are measured. The primary efficacy analysis described in [Section 0](#) models the number of body regions with new HO compared to the previous scan and the volume of new HO within each body region with new HO compared to the previous scan as the unit of measurement.

Note that the primary endpoint includes annualized HO based on the new HO observed up to Month 24 in MOVE and up to Month 36 in NHS. The sponsor believes that the new HO observed between Month 24 and Month 36 in NHS is relevant and that annualization is sufficient to protect against bias. Sensitivity analyses to assess impact of differences in length of follow-up between NHS and MOVE are described in [Section 2.4.4](#).

The primary efficacy endpoint, as well as the secondary endpoints that depend on the efficacy imaging, will not be summarized in the descriptive analysis to be conducted before the first formal interim efficacy analysis, due to the ongoing nature of the blinded reads.

Secondary Efficacy Endpoints

The following secondary efficacy endpoints will be assessed:

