The new HO volume (square-root of the volumetric increase in that region) in region r , $\sqrt{Z_{ijr}}$, where new HO has occurred for subject i in scan j is assumed to be distributed as:

$$\sqrt{Z_{ijr}}/1000 \sim N\left(\alpha * \alpha_r * \theta_{2,t(ij)}, \frac{\alpha_r^2}{\tau_{t(ij)}}\right).$$

The scale of new HO volume is modeled in the thousands. Letting $\theta_{2,0} = 1$, the variable $\theta_{2,1}$ is the multiplicative effect of palovarotene treatment on the new HO volume conditional on new HO occurring. The α_r are region-specific variables that contribute to the mean of new HO and the variance; the restrictions $\alpha_r = \alpha_{r'}$, where r and r' are a left and right region pair are included, i.e., right chest and left chest, right arm and left arm, right hip and left hip, and right lower leg and left lower leg. The precision variables, τ_0 and τ_1 , introduce flexibility by allowing variability to differ between new HO volume in treated subjects and untreated subjects.

The prior distributions for the variables in the Bayesian compound Poisson distribution are the following:

$$\begin{aligned}\lambda_i &\sim \text{Gamma}(a, \text{scale} = b) \\ \beta_1, \beta_2 &\sim N(0, 2^2) \\ a, b &\sim \text{Gamma}(1, 1) \\ \alpha &\sim N(0, 1) \\ \alpha_r &\sim \text{Unif}(0, 4) \\ \tau_0, \tau_1 &\sim \text{Gamma}(1, 0.01) \\ \theta_{1,1}, \theta_{2,1} &\sim \text{Unif}(0, 2).\end{aligned}$$

All gamma distributions are parameterized as the shape and rate, except as noted for λ_i . The primary efficacy analysis comparing the annualized change in new HO volume between subjects treated with palovarotene and untreated subjects is performed by calculating the ratio of the annual mean change in HO volume in palovarotene treated subjects to untreated subjects using the Principal FAS and assuming missing at random.

In this SAP, new HO is deemed to be present in a body region if the volume of net new HO is greater than zero, i.e., the change in volume of HO in a region between two timepoints is positive. (Volumes of individual lesions are not assessed; the net volume of HO in a body region is reported.). Any regions with amounts of new HO $< 0 \text{ mm}^3$, i.e., reductions in the volume of HO over time (which can happen due to bone remodeling or measurement variability), will be represented as having no new HO and the volumes will be set to zero in the analysis.

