For these reasons, while acknowledging that it is post-hoc, the sponsor believes that the Bayesian compound Poisson analysis without the square-root transformation is the more appropriate analysis of the primary endpoint, relative to the Bayesian compound Poisson analysis with the square-root transformation. The Bayesian analysis without square root transformation is referred to as the analysis of primary interest.

When performed without the square-root transformation, the new HO volume in region r , Z_{ijr} , where new HO has occurred for subject i in scan j is assumed to be distributed as:

$$Z_{ijr}/1000 \sim N\left(\alpha * \alpha_r * \theta_{2,t(ij)}, \frac{\alpha_r^2}{\tau_{t(ij)}}\right).$$

The prior distributions for the variables in this Bayesian compound Poisson distribution are the following:

$$\begin{aligned} \lambda_i &\sim \text{Gamma}(a, \text{scale} = b) \\ \beta_1, \beta_2 &\sim N(0, 2^2) \\ a, b &\sim \text{Gamma}(1, 1) \\ \alpha &\sim N(0, 10^2) \\ \alpha_r &\sim \text{Unif}(0, 4) \\ \tau_0, \tau_1 &\sim \text{Gamma}(1, 100) \\ \theta_{1,1}, \theta_{2,1} &\sim \text{Unif}(0, 2). \end{aligned}$$

The Bayesian compound Poisson model will be fitted using the R statistical computing language and environment. The R programs will be run using v3.5.0 or later; packages used, including version number, will be identified in the CSR.

Additional supportive analyses including the weighted mixed linear effect (wMLE) analysis with and without the square-root transformation will also be performed. The wLME analysis without the square-root transformation was previously the primary efficacy analysis, before the Bayesian compound Poisson analysis was added in Amendment 1 of the protocol. This wLME analysis without square-root transformation is referred to as the alternative analysis of primary interest.

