Please note that, as referenced above, the Bayesian compound Poisson models with and without square-root transformation assume non-negative changes in HO volume for each subject for each region, and any apparent reductions in HO volume over time (i.e., negative new HO volumes) are “zeroed out”, i.e., replaced with zero. (All analyses of square-root transformed new HO volumes require non-negative new HO volume in order for the square-root transformation to be applied.) In contrast, because wLME is a regression method, it is less specialized and can accommodate the negative values when applied to non-transformed data.

However, in order to understand the relative contributions to the results of 1) zeroing out the negative changes; 2) square-root transformation of the zeroed out new HO volumes; 3) using a body-region or overall whole body based analysis; 4) using data on intervals between WBCTs, not just the first and last timepoint; 5) Bayesian compound Poisson analysis; we will run five wLME “series”:

1. Raw, untransformed data (i.e., including all negative values)
2. Zero out overall whole-body new HO without square-root transformation
3. Zero out overall whole-body new HO with square-root transformation
4. Zero out by region [by visit] without square-root transformation
5. Zero out by region [by visit] with square-root transformation

For series 2 and 3, the sum of new HO at the last timepoint, i.e., changes from baseline including negatives, is added across body regions. If negative, the sum is replaced with zero. For series 3, the sum is square-root transformed. Then the sum – or square-root of the sum – is divided by time in years, resulting in the annualized new HO.

For series 4 and 5, negative changes in HO volume by region (from previous visit) are replaced with 0. For series 5, the square-root of each change is taken. These numbers are then added across timepoints and body regions and their sums are divided by time in years, resulting in annualized new HO. This method for constructing annualized new HO, with and without square-root transformation, yields wLME analyses that are the closest analogs to the Bayesian compound Poisson analyses.

Note that in applying the square-root transformation to zeroed out new HO for intervals, wLME using series 5 should be subject to the same bias as is attributed to the Bayesian compound Poisson primary analysis illustrated later in this section.

Control of Type I Error

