- Analysis using generalized estimating equations (GEE): A GEE model will be fit to the annualized change in new HO and the empirical variance estimator will be used for inference. Weights will be used to account for the different lengths of observed subject follow-up. Baseline HO volume divided by age will be included in the model as a covariate and a compound-symmetric working correlation matrix will be used. The GEE model takes a different approach to account for within-subject correlation compared to the primary analysis.

To assess consistency of efficacy signal across subgroups:

- Subgroup analyses: The subgroup analyses will also be performed for all efficacy endpoints to examine the consistency of the estimated treatment effect by sex (Male, Female), Asian ancestry (Yes, No), and age (≥ 12 , ≥ 14 , ≥ 18 , $\geq 12 - < 17$ years) and age by sex (< 8 years for Females or < 10 years for Males; ≥ 8 years for Females or ≥ 10 years for Males; $\geq 8 - < 14$ for Females or $\geq 10 - < 14$ years for Males).

The inferential analysis method used in the subgroup analyses will be Bayesian compound Poisson analysis and wLME for new HO volume by age and age by sex, and for wLME for all other endpoints and factors, with the exception of the above

contingency table analysis of proportions of subjects with new HO and flare-ups; this analysis will employ Fisher's exact test.

To assess impact of the difference in WBCT visit schedules between MOVE and NHS:

- The impact of the difference in WBCT visit schedules between MOVE and NHS is assessed by analyzing the data as if the WBCT assessments in MOVE were conducted annually rather than biannually. This is intended to investigate whether the differences in visit schedules introduced bias, with and without use of the square-root transformation. Estimates of γ , $\theta_{1,1}$, $\theta_{2,1}$ will be compared between Bayesian compound Poisson analyses, with and without square-root transformation, with the observed biannual MOVE WBCT and with the dataset collapsed to simulate annual MOVE WBCT assessments.

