It must be noted, however, that this analysis does not eliminate the effect of the more frequent assessments in MOVE; as described in the MOVE and NHS Independent Review Charter, radiologists only measured the amount of HO if they first determined there was new HO relative to the previous timepoint. If there was no new HO, the volume from the previous assessment was carried forward. Because the read process for the 12-month timepoint used the 6-month assessment and the read process for the 24-month assessment used the 18-month assessment, this analysis can investigate only the bias introduced by the differences in visit schedules into the analysis, not the differences in visit schedules per se.

In any case, the sponsor believes that the differences in visit schedules could result in biases of the event rate treatment effect $\theta_{1,1}$ against palovarotene and growth rate treatment effect $\theta_{2,1}$ in favor of palovarotene but that, in the absence of the square-root transformation, these biases are offset, yielding an unbiased estimate of $\gamma = \theta_{1,1} * \theta_{2,1}$.

With the square-root transformation, however, the bias against palovarotene in the event rate treatment effect $\theta_{1,1}$ is unchanged, while the bias on growth rate treatment effect $\theta_{2,1}$ in favor of palovarotene is reduced, yielding a bias in γ against palovarotene.

Consider identical growth events in NHS and MOVE of 8000 mm³ that is split across two six-month intervals in the MOVE study as 4000 mm³ in the first 6-month interval and 4000 mm³ in the next 6-month interval. This registers as two events in one year on MOVE, but just one event in NHS. Similarly, the growth rate, conditional on there being an event, is 2X higher in NHS than MOVE, i.e., 8000/4000=2, in the absence of a square-root transformation. With a square-root transformation, however, the growth rate per event is only 1.4X higher in NHS than MOVE, i.e., $\sqrt{8000}/\sqrt{4000} \sim 1.41$.

A similar comparison of analyses will be performed with wLME, where negative values are zeroed out by region and then square-root transformed, because the bias illustrated above from the square-root transformation should also affect this annualized HO endpoint, which is constructed using new HO observed at each visit.

Analyses of Secondary Efficacy Endpoints

Proportion of Subjects with Any New HO (Key Secondary Endpoint) and Number of Body Regions with New HO

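### The SAP calls the untransformed γ unbiased under unequal scan schedules, but zeroing negative regional changes at each interval breaks the offset it relies on; the effect is probably small

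*SAP*

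**What the plan says.** SAP Section 2.1.3 sets different schedules. After the first two NHS scans (at entry and one year later), its list continues with "Month 24 and Month 36 in the NHS and at baseline, Month 6, Month 12, Month 18 and Month 24 in the MOVE Trial". The model works from the number of regions with new HO and "the volume of new HO within each body region with new HO compared to the previous scan as the unit of measurement".

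Section 2.4.4 (Primary Analysis) says of falls in regional volume that they "can happen due to bone remodeling or measurement variability), will be represented as having no new HO and the volumes will be set to zero". Under Handling of Reductions in HO it adds that "the Bayesian compound Poisson models with and without square-root transformation assume non-negative changes in HO volume for each subject for each region".

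Section 2.4.4 (Sensitivity Analyses) gives the sponsor's belief that the schedule difference biases θ1,1 (event rate) against palovarotene and θ2,1 (volume per event) in its favour, but that "in the absence of the square-root transformation, these biases are offset, yielding an unbiased estimate of" γ = θ1,1 × θ2,1. The support is one worked example, a growth of 8000 mm³ that MOVE sees as 4000 + 4000. The planned check compares fits to the observed MOVE data with fits "with the dataset collapsed to simulate annual MOVE WBCT assessments". How a regional change is formed in the collapsed dataset is not stated.

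The same subsection describes the reading rule: a volume is measured only if the radiologist first sees new HO since the previous scan, and otherwise the earlier volume is kept.

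In Section 2.4.4 (Additional Analyses), schedule bias under the square root is one of three reasons for a choice that the SAP acknowledges is post hoc: "the sponsor believes that the Bayesian compound Poisson analysis without the square-root transformation is the more appropriate analysis of the primary endpoint".

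**The concern.** The offset is an additivity argument. Splitting one growth into two readings doubles the count and halves the mean volume, so the product is unchanged. Once negative changes are replaced by zero, changes no longer add up across scans, and the replacement happens twice a year in MOVE and once in NHS. The SAP's example contains no negative change, so it does not meet the case, although the SAP itself expects negatives.

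At stake is a stated property that helps to justify the analysis of primary interest, chosen after unblinding. The argument sets a biased analysis against an unbiased one, and the second half lacks its conditions. The planned check could also miss the problem. If the collapsed dataset sums half-year changes that are already zeroed, MOVE's annual total is unchanged by construction, and the untransformed γ would hardly move whether or not it was biased.

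**Working it through.** **1. The SAP's example.** MOVE/NHS event ratio = 2/1 = 2. Untransformed volume ratio = 4000/8000 = 0.5, so γ = 2 × 0.5 = 1.00. With the square root, the volume ratio is √4000/√8000 = 0.707, so γ = 2 × 0.707 = 1.41. Both agree with the SAP's 2X and 1.41.

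**2. Effect of zeroing.** For half-year changes a and b in one region, max(0,a) + max(0,b) ≥ max(0,a+b). The inequality is strict when a and b have opposite signs and an equality otherwise. Extra zeroing can therefore raise MOVE's annual total relative to NHS but never lower it.

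**3. The example with read noise.** Assume independent normal error with the same SD at each scan. A change then has SD s = √2 × SD, and E[max(0,X)] = mΦ(m/s) + sφ(m/s) for true change m. At a per-scan SD of 4,000, s = 5,657:
- m = 4000: 4000 × 0.7602 + 5657 × 0.3107 ≈ 4,799; two intervals give about 9,597.
- m = 8000: 8000 × 0.9214 + 5657 × 0.1468 ≈ 8,201.
- Ratio = 9,597/8,201 = 1.17.

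At SDs of 500, 1,000 and 2,000 the ratio is 1.000, 1.000 and 1.025. Noise too small to turn a change negative adds almost nothing.

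**4. Simulation with no treatment effect (true γ = 1).** Inputs from SAP Table 1 (Section 1.7): regional event proportions and gamma volumes from the tabulated means and SDs, with SD equal to the mean for elbow, hand and wrist. Each run has 200,000 subject-years and applies the reading rule. Assumed: the per-scan SD, the share of growth that spans both half-years, and the false-call and missed-growth settings. γ is taken as the ratio of annual totals.

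| Scenario under the reading rule | SD 250 | SD 1,000 | SD 2,500 | SD 5,000 |
|---|---|---|---|---|
| No growth spans both half-years | 1.000 | 1.000 | 1.000 | 1.000 |
| Half spans | 1.000 | 1.003 | 1.011 | 1.029 |
| All spans | 1.001 | 1.006 | 1.022 | 1.058 |
| Half spans, 5% false calls per region and scan | 1.004 | 1.016 | 1.042 | 1.088 |
| All spans, growth under 2,000 mm³ per interval missed | 0.992 | 0.992 | 0.994 | 1.006 |
| All spans, growth under 5,000 mm³ per interval missed | 0.973 | 0.973 | 0.973 | 0.976 |

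**5. The collapse rule.** Take a > 0 > b. Summing zeroed half-year changes gives a, the same as the six-monthly data. Netting first and then zeroing gives max(0, a+b), which is smaller. Only the second mimics an annual scan.

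**The case against.** The strongest objection is the reading rule. A stable region that the radiologist calls stable contributes exactly zero, so its measurement error never enters. If growth falls within one half-year and the other is carried forward, both schedules give the same distribution and γ stays at 1. This stands, and it is why the size is small.

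The SAP also words the claim as a belief and does not ignore zeroing. It tabulates the frequency of negative changes. It plans wLME series that keep all negatives (series 1), zero once on the whole-body change (series 2) or zero by region and visit (series 4). It names the untransformed wLME as the alternative analysis of primary interest. These are useful context. However, series 1 and 4 differ in zeroing, in unit of analysis and in use of interim scans all at once, and none of them corrects the Bayesian γ.

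The natural reading of data treated as if scanned annually is Month 12 minus baseline, zeroed once. That is probably what was intended, so the request is mainly to write it down.

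The preference for the untransformed model largely survives. In the SAP's own example the square root gives 1.41, against about 1.00 to 1.06 in the simulation without false calls or missed growth. The other two reasons, the data monitoring committee's observation and power for catastrophic HO, are untouched. The zeroing bias works against the drug, and no success thresholds now apply. These points limit the importance of the matter but do not make the unqualified statement correct.

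**Conclusion.** The statement that the untransformed γ is unbiased does not hold in general. It needs no negative regional change and equal detection of growth on both schedules. Where a re-measured region has interval changes of opposite sign, per-interval zeroing can only raise MOVE relative to NHS.

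Under the documented reading rule the effect is about 0% to 6% on γ for assumed per-scan SDs up to 5,000 mm³, and up to about 9% with 5% false calls. The documents give no measurement SD and no false-call rate. The only hint of scale is the pair of reader-discrepancy limits in SAP Section 2.1.5 (10,000 and 25,000 mm³), which are not SDs. The figures are ratios of annual totals, not Gibbs fits of the SAP model. They also take every NHS interval as 12 months, whereas the sample-size assumptions in Section 1.7 include 1.5-year NHS scans.

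A reader might infer that any measurement noise biases γ against palovarotene, and heavily. Re-measuring every region at every scan would give 1.06 to 1.59 at SDs of 250 to 5,000, but that contradicts the carry-forward rule. A reader might also infer that the net schedule bias must be against the drug. The documents do not support that either: growth missed at half-year reads gives about 0.97 to 1.01, so the net sign is not fixed.

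**What to change.** 1. In Section 2.4.4 (Sensitivity Analyses), replace the unbiasedness statement with its conditions: the offset holds only if no regional change is negative and reads detect growth equally on both schedules; zeroing at each interval, taken alone, biases γ against palovarotene.
2. Define the collapsed dataset there: for each region, the signed net change from the start to the end of each 12-month window, zeroed once after netting, not the sum of half-year changes already set to zero.
3. Show the untransformed annual-collapse γ, which is already planned, beside the analysis of primary interest. Give the frequency of negative changes and untransformed wLME series 1, 2 and 4 as context.

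The SAP treats the third interim analysis as final for efficacy, plans no later Bayesian analyses and does not intend to rerun interim-report analyses. It is therefore enough to disclose the collapse rule used then and to rerun that one dataset only if zeroed changes were summed. The cost is a wording change, one derivation rule and at most one rerun. The downside is slightly fewer MOVE event intervals in that sensitivity run.

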1.10 Statistical Modifications to the Statistical Analysis Plan

1.10.1 Statistical Modifications to the Statistical Analysis Plan, V1.0

The primary and secondary efficacy analyses described in Protocol Amendment 1 do not include explanatory covariates. Because recent studies – Clementia’s NHS as well as other studies – suggest that age may be important for flare-up rate and the formation of new HO, age (<18, ≥18 years) and additional categorical variable sex (Male, Female) is included in the primary and secondary efficacy analyses.

The analysis of the secondary endpoints proportion of subjects with any new HO and number of body regions with new HO will both be conducted using the Bayesian compound Poisson model used in the primary efficacy analysis; in fact, the inference is identical for these two secondary endpoints. Within the compound Poisson model, $\theta_{1,1} < 1$ implies both a lower proportion of subjects with any new HO and a smaller number of body regions with new HO for palovarotene-treated subjects.

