1.10.3 Statistical Modifications to the Statistical Analysis Plan, V1.2

SAP Version 1.2 introduces the following changes:

- Clarifies that drawing subject-level rates of body regions with new HO from a gamma distribution and then drawing from Poisson distributions using these subject-level rates implies that the marginal distribution of the number of body regions with new HO follows a negative binomial distribution, which requires much less restrictive assumptions than a Poisson distribution and does not tend to result in an underestimate of the variance.
- Notes that additional details of the operating characteristics of the Bayesian compound Poisson analysis, including its chance of producing erroneous conclusions and the reliability of treatment effect estimates, will be included in a separate simulation report.
- Clarifies the secondary and exploratory endpoint definitions to add timepoints at which the endpoints will be compared between NHS and MOVE.
- Clarifies the definitions of treatment-emergent AEs and post-treatment AEs.
- Removes summaries of retinoid-associated AEs, as they already appear in the AE tables.
- Clarifies that a listing of traumas leading to flare-up will be generated.
- Adds summaries of imaging performance, i.e., intra-reader agreement and inter-reader agreement, and quality metrics.
- Adds summaries of dosing compliance.
- Clarifies the wLME analysis method by adding pseudocode.
- Clarifies the methods used to prepare the dataset for application of the Bayesian compound Poisson analyses and square-root transformation, including the methods used to ‘zero out’ negative changes in HO volume.
- Clarifies the purpose, timing and conduct of the sensitivity analyses.
- Updates the list of subgroups to be studied to be consistent with feedback from FDA.
- Adds analyses for the HO-based secondary analyses and simplifies the analyses of the flare-up-based secondary endpoints.
- Adds summaries of growth velocity.
- Summarizes duration of flare-up treatment and duration of non-flare-up treatment, which are used in the summary of compliance.

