The proportion of subjects with any net new HO (at Month 12) – and number of body regions with any net new HO (at Month 12) – will be compared between the MOVE and NHS groups using the Bayesian compound Poisson model used in the primary efficacy analysis. (New HO is deemed to be present in a body region qualitatively if the volume of net new HO is greater than zero, i.e., the change in volume of HO in a region between two timepoints is positive when new HO is identified qualitatively) Gibbs sampling from the posterior distribution will be generated to compute the posterior distribution of $\theta_{1,1}$, the multiplicative effect of palovarotene treatment on the rate of body regions with new HO. Because, within the compound Poisson model, $\theta_{1,1} < 1$ implies both a lower proportion of subjects with any new HO and a smaller number of body regions with new HO for palovarotene-treated subjects, the inference is identical for these two secondary endpoints. The probability of this ratio being less than 1 must be greater than 0.975 to declare statistical significance.

Inference on $\theta_{1,1}$ from the sensitivity analysis analyzing the data as if the WBCT assessments in MOVE were conducted annually rather than biannually will also be relevant, given the concerns about bias in estimating $\theta_{1,1}$ even in the absence of square root transformation will be summarized.

Tables will be provided summarizing the number and percentage of subjects with any net new HO by study visit and overall. In these tables, Month 12 incidence will be compared using an exact test for the difference in proportions.

Tables will also be provided summarizing the number of body regions with new HO by study visit and overall. The body regions with new HO will also be summarized by study visit and overall. In these tables, Month 12 counts will be compared using a negative binomial regression.

Flare-up Rate Per Subject-Month Exposure

The flare-up rate per subject-month exposure will be compared using a negative binomial regression on the number of flare-ups. An offset variable equal to the log of the number of years of follow-up will be included to convert the estimate to annualized rate.

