In the NHS study, events were considered flare-ups when two or more flare-up signs were reported. This is different from the MOVE study, which defines a flare-up as an event with one or more flare-up sign. The analysis of the proportion of subjects reporting flare-ups will restrict the MOVE flare-ups to those events that match the NHS study definition.

Descriptive tables will be provided summarizing the number of flare-ups and the rate of flare-ups by study visit, by age group and overall.

Proportion of Subjects Reporting Flare-ups

The proportion of subjects reporting flare-ups will be compared between untreated and treated subjects using an exact test for the difference in proportions.

As with flare-up rate analysis, this analysis will be performed restricting the MOVE flare-ups to those events that match the NHS study definition.

Descriptive tables will be provided summarizing the number and percentage of subjects with any flare-up by study visit, by age group, and overall.

Analyses of Exploratory Endpoints

The exploratory efficacy endpoints, including change from baseline in CAJIS Total score, CAJIS Upper Extremities subscore and CAJIS Mobility subscore; FOP-PFQ total score; and PROMIS Global Physical Health and Global Mental Health T-scores; will be summarized by visit using descriptive statistics for the Principal FAS and presented for the Supplementary FAS in listings.

Additional exploratory endpoints of incidence and volume of “catastrophic HO” will also be described and compared between MOVE and NHS for the Principal FAS. It has been observed – after unblinding at the second interim analysis – that a minority of subjects develop large amounts of HO in a year; the incidence of subjects with at least 50,000 mm³ and 30,000 mm³ of new HO across all body regions in each year of study will be summarized.

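### The two flare-up secondary endpoints are compared between non-randomised groups (MOVE and NHS) with no age or sex adjustment specified

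*SAP*

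**What the plan says.** Flare-up rate and the proportion of subjects with flare-ups are two of the four secondary endpoints (SAP 2.1.3). Together they serve the first secondary objective (SAP 1.6.2).

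SAP 2.4.4 gives the methods. For the rate: "The flare-up rate per subject-month exposure will be compared using a negative binomial regression on the number of flare-ups", followed by "An offset variable equal to the log of the number of years of follow-up will be included to convert the estimate to annualized rate". For the proportion: "The proportion of subjects reporting flare-ups will be compared between untreated and treated subjects using an exact test for the difference in proportions". No age term, sex term or stratum is named for either.

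Elsewhere the SAP treats age and sex as worth adjusting for:

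- The compound Poisson model in 2.4.4 includes sex and age (<18, ≥18) in the rate of body regions with new HO. The same model serves the two HO-based secondary endpoints.
- The V1.0 entry of the modification history (1.10.1) explains why these variables were added: recent studies "suggest that age may be important for flare-up rate and the formation of new HO".
- The V1.2 entry (1.10.3) records a later change: "Adds analyses for the HO-based secondary analyses and simplifies the analyses of the flare-up-based secondary endpoints".

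The covariate-adjusted and propensity-score sensitivity analyses in 2.4.4 are set up to test the robustness of the new-HO analysis. Flare-ups receive descriptive tables by age group and a place in the subgroup analyses.

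**The concern.** The comparison is between a single-arm trial and an external control, and Protocol 6.3 confirms that there is no randomisation. Any baseline variable that differs between the groups and also drives flare-ups will move a crude contrast. The SAP itself names age as a candidate for flare-up rate, adjusts for it when modelling new HO, and then specifies no adjustment for flare-ups. It gives no reason why adjustment is unnecessary here.

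At stake is how two secondary endpoints are read. A crude rate ratio away from 1 could reflect a different age mix rather than palovarotene. Equally, a real effect could be masked. The primary analysis is not affected. This is a question of confounding, separate from the correlation that arises because some subjects contribute to both studies.

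**Working it through.** **No figure to reproduce.** The documents give no effect size, power or alpha for the flare-up comparisons, and neither the share of subjects under 18 nor flare-up rates by age. The size below therefore rests on stated assumptions.

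**Step 1: what adjusts the overall flare-up contrast.**

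| Planned analysis (SAP 2.4.4) | Covers flare-ups? | Adjusts the overall contrast for age and sex? |
|---|---|---|
| Negative binomial regression | Yes | None named |
| Exact test of proportions | Yes | No; no strata named |
| Compound Poisson model with age and sex | No, new HO only | Not applicable |
| Additional covariates; propensity score | No, new HO only | Not applicable |
| Tables by age group | Yes | No, descriptive |
| Subgroups by sex, age, age by sex | Yes | No, splits the data |

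The listed age subgroups (≥12, ≥14, ≥18, ≥12 to <17) overlap and include no under-18 group, so they cannot be recombined into an estimate stratified at 18.

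**Step 2: crude rate ratio with no drug effect.** Let k be the flare-up rate under 18 divided by the rate at 18 and over, and let pM and pN be the shares under 18 in MOVE and NHS. Then

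crude ratio = (1 + pM(k − 1)) / (1 + pN(k − 1)).

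Assumed: pN = 0.60 and k = 1.5, 2 or 3.

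| pM | k = 1.5 | k = 2 | k = 3 |
|---|---|---|---|
| 0.60 | 1.00 | 1.00 | 1.00 |
| 0.50 | 1.25/1.30 = 0.96 | 1.50/1.60 = 0.94 | 2.00/2.20 = 0.91 |
| 0.40 | 1.20/1.30 = 0.92 | 1.40/1.60 = 0.88 | 1.80/2.20 = 0.82 |
| 0.70 | 1.35/1.30 = 1.04 | 1.70/1.60 = 1.06 | 2.40/2.20 = 1.09 |

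**Step 3: effect on the test.** Negative binomial data were simulated with no drug effect, 600 runs per cell. Inputs from the documents:

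- 90 NHS subjects, 45 followed for 1.5 years and 45 for 2 years (SAP 2.4.4, Control of Type I Error).
- 99 MOVE subjects, each followed for 2 years (same place).
- Two flare-ups per year, borrowed from the expected treated flare-ups in Protocol 7.2.6.

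Dispersion 1 is assumed. Two-sided rejection at 5% without adjustment:

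| pM (pN = 0.60) | k = 1.5 | k = 2 | k = 3 |
|---|---|---|---|
| 0.60 | 4.0% | 5.2% | 5.2% |
| 0.50 | 4.7% | 7.8% | 9.3% |
| 0.40 | 7.3% | 15.0% | 21.5% |
| 0.70 | 4.7% | 6.8% | 8.8% |

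Adding one age term (<18, ≥18) returned the rate ratio to 0.99–1.01 and rejection to 3.7%–6.0% in every cell. The standard error at 5% is √(0.05 × 0.95/600), about 0.9 points, so these are close to nominal. The simulation treats the groups as independent and ignores subjects who are in both studies. The corresponding bias in the proportion endpoint was not computed.

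**The case against.** A reader might infer that the SAP contradicts itself, because the V1.0 entry says of age and sex that "additional categorical variable sex (Male, Female) is included in the primary and secondary efficacy analyses". The documents do not support that. The entry belongs to a modification history, and the V1.2 entry records that the flare-up analyses were later simplified. The V1.0 text is useful only as evidence of why age was thought relevant. It also says only that age may be important. It does not say that flare-ups depend on age or that adjustment is necessary, and the flare-up method in Protocol 8.5.2.2 names no covariates.

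Several other points have weight:

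- The regression sentence is not a full specification; it does not name a treatment term either. Age and sex might be intended. The exact test leaves less room, since a two-group comparison has no place for them. Either way, the text needs to say what is fitted.
- Existing plans would expose an imbalance. Demographics by treatment group include age groups and sex (SAP 2.1.1, 2.4.1), and flare-ups are tabulated by age group and analysed by subgroup. This stands as mitigation, but seeing an imbalance is not the same as adjusting for it.
- Overlap limits the likely gap. Planning assumed that about 45 of 80 MOVE subjects would come from NHS (SAP 1.7). If they had the same age split as NHS, an overall gap of 10 points would need 10 × 80/35 ≈ 23 points among the other 35, and a gap of 20 would need about 46. Against that, each crossover subject is older in MOVE than in NHS. The net imbalance is unknown.
- After the second interim analysis, no success or futility thresholds apply to efficacy analyses (SAP 2.4.4). The rejection rates above therefore illustrate interpretation and do not describe a formal error rate.

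**Conclusion.** The point holds as a missing adjustment. Both flare-up comparisons are specified without age or sex in a non-randomised design, and no adjusted flare-up analysis is planned elsewhere.

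Its size is conditional. With 60% of NHS under 18 and k from 1.5 to 3, a 10-point shortfall of under-18s in MOVE gives a crude rate ratio of 0.91–0.96 with no drug effect, a modest bias of about 4% to 9%. A 20-point shortfall gives 0.82–0.92. If MOVE is 10 points younger, the ratio is 1.04–1.09, and with equal age mixes there is no bias from this source. A reader might take this as showing that the flare-up results are biased towards palovarotene. The documents do not support that, because they give neither the age split nor the age-specific rates, and the direction could be either way.

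The change is worth making because it is cheap and matches how the SAP already handles new HO.

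**What to change.** Add to SAP 2.4.4, as supplementary analyses:

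1. For the rate, the negative binomial model with treatment, age (<18, ≥18 at start of follow-up), sex and the existing offset.
2. For the proportion, a logistic model with treatment, age and sex, or an exact test stratified by age and sex.

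Report these beside the current comparisons, and label the current ones unadjusted.

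No new data are needed, since the new-HO model already uses age and sex for both studies. The cost is a short SAP addition and a small amount of programming. The downside is timing. V1.2 was written after the third interim analysis, and the sponsor was unblinded after the second, so the adjusted analyses must be labelled as specified after unblinding. SAP 3.3 says interim-CSR analyses are not planned to be rerun, but it leaves room for further analyses, so a supplement fits without reopening what has been reported.
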